8.6.2. Clinical Laboratory Parameters

All clinical laboratory parameters, with changes from baseline, will be listed; any value outside the clinical reference range will be flagged, and whether the out of range value was deemed clinically significant or not clinically significant will be indicated.

The observed results and change from baseline for clinical chemistry, hematology, and coagulation parameters will be summarized descriptively by timepoint. Values recorded as $\text{<}x$, $\leq x$, $\geq x$, or $\text{>}x$ will be displayed in the listings as recorded. For the derivation of listing flags, calculation of summary statistics, $\text{<}x$ and $\leq x$ values will be set to 0, whereas $\geq x$ and $\text{>}x$ values will be set to x.

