Appendix 2: Clinical Laboratory Evaluations

Clinical Chemistry Panel (Fasted):	Hematology Panel:	Other Tests:
Alanine aminotransferase (ALT)	Hematocrit	Hemoglobin A1c (HbA1c) ^b
Albumin	Hemoglobin	Thyroid-stimulating hormone (TSH) ^b
Alkaline phosphatase (ALP)	Mean corpuscular hemoglobin	Estimated glomerular filtration rate ^{a,d}
Amylase	Mean corpuscular hemoglobin concentration	SARS-CoV-2 (COVID-19) test
Aspartate aminotransferase (AST)	Mean corpuscular volume	Coagulation Parameters:
Bilirubin (direct and total)	Platelet count	Partial thromboplastin time
Blood urea nitrogen	Red blood cell (RBC) count	Prothrombin time
Calcium	RBC distribution width	International normalized ratio
Chloride	White blood cell (WBC) count	
Cholesterol	WBC differential (percent and absolute):	Serology: ^b
Creatine kinase	Basophils	Hepatitis B surface antigen (HBsAg)
Creatinine	Eosinophils	Hepatitis B virus (HBV)
Glucose	Lymphocytes	immunoglobulin M (IgM) core antibody
Iron	Monocytes	Hepatitis C virus (HCV) antibody
Lipase	Neutrophils	Human immunodeficiency virus (HIV) antibody
Magnesium		
Phosphorus		
Potassium		
Sodium		
Total protein		
Triglycerides		For Female Subjects Only:
Uric acid		Pregnancy test (serum qualitative, serum quantitative may be used for confirmation if needed) ^c
		Follicle-stimulating hormone (post-menopausal female subjects only) ^b
Urine Drug Screen:^a		
Including but not limited to the following:		
Alcohol (ethanol) ^e	Bilirubin	
Amphetamines	Color and appearance	
Barbiturates	Glucose	
Benzodiazepines	Ketones	
Cannabinoids	Leukocyte esterase	
Cocaine (metabolite)	Nitrite	
Methadone	Occult blood	
Opiates	pH and specific gravity	
Phencyclidine	Protein	
Cotinine	Urobilinogen	
	Microscopic examination including bacteria, casts, crystals, epithelial cells, RBCs, and WBCs (if protein, leukocyte esterase, nitrite, or occult blood is positive)	

- a. Performed at Screening and Check-in (Day -1) only.
- b. Performed at Screening only.
- c. Performed at Screening, Check-in (Day -1), and Day 22 for End of Treatment (EOT) or Early Termination (ET) only.
- d. Calculated using the Chronic Kidney Disease Epidemiology Collaboration (CKD-EPI) equation.
- e. Urine or breath test.

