8.6.5. Other Assessments

Medical history and physical examination will be listed. Any physical examination abnormalities reported will also be flagged as clinically significant or not clinically significant as indicated.

All other safety and tolerability assessments not detailed in the above sections will be listed only.

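### Laboratory results reported below a limit are counted as 0, which can put impossible values into coagulation summaries and unsupported low flags into listings

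*SAP*

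**What the plan says.** SAP 8.6.2 (Clinical Laboratory Parameters) sets the rule. Results recorded with an inequality sign "will be displayed in the listings as recorded", but a number replaces them in derivations. The scope is given as "For the derivation of listing flags, calculation of summary statistics". Within that scope, for `<x` and `≤x`, "values will be set to 0, whereas" results recorded as `≥x` or `>x` become x.

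Two outputs depend on the rule:

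- **Summaries.** "The observed results and change from baseline for clinical chemistry, hematology, and coagulation parameters will be summarized descriptively by timepoint". Protocol Appendix 2 lists partial thromboplastin time, prothrombin time and "International normalized ratio" as the coagulation parameters.
- **Flags.** For all laboratory parameters, "any value outside the clinical reference range will be flagged".

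Urinalysis is not among the summarized panels, and SAP 8.6.5 adds that "All other safety and tolerability assessments not detailed in the above sections will be listed only". Neither document limits the substitution to analytes that can be near 0, and no other section corrects it.

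**The concern.** Zero is a fair stand-in for `<x` only when x is itself close to 0. INR, prothrombin time and partial thromboplastin time cannot be 0, yet they fall under the same rule as everything else. A single such result would set the minimum of a small table to an impossible value, inflate the SD and give that subject a large artificial change. If the baseline is the censored value, the artificial change is a rise; if a later value is censored, it is a fall. Results censored at the upper end do not have this problem, because they take x.

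The flags are affected too. Zero lies below any positive LLN, so every `<x` or `≤x` result on such an analyte is flagged low, whether or not the record shows that it is low.

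At stake is the readability of the laboratory safety tables and listings, which serve a secondary endpoint. The trial has up to 16 subjects (Protocol 8.1), and additional sites use their local laboratories (Protocol, study identification pages), so x and the reference limits may differ by site.

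**Working it through.** The plan gives no figure of its own on this point, so there is nothing to reproduce. The check applies the rule as written.

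**Inputs from the documents.** The substitution rule is in SAP 8.6.2. Change from baseline is the timepoint value minus the baseline value (SAP 8.1.3). The sample is n = 16, the maximum in Protocol 8.1.

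**Assumed inputs.** INR reporting limit x = 0.9 (range 0.8 to 1.0), all other INR values 1.0, and the LLN values below. The documents give neither reporting limits nor reference ranges.

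**Step 1: one censored INR among 16.** With s substituted for `<0.9`, mean = (15 × 1.0 + s)/16 and SD = (1.0 − s)/√16.

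| Substituted s | Mean | SD | Minimum | Change from a baseline of 1.0 |
|---|---|---|---|---|
| 0 (SAP rule) | 15.00/16 = 0.938 | 1.00/4 = 0.250 | 0 | −1.0 |
| x/2 = 0.45 | 15.45/16 = 0.966 | 0.55/4 = 0.138 | 0.45 | −0.55 |
| x = 0.9 | 15.90/16 = 0.994 | 0.10/4 = 0.025 | 0.9 | −0.1 |

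One result makes the SD ten times as large as it is with x.

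**Step 2: range.** Relative to substituting x, the rule shifts the mean by −k·x/16 for k censored results. For x = 0.8, 0.9 and 1.0:

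- k = 1: −0.050, −0.056 and −0.063.
- k = 4: −0.200, −0.225 and −0.250.

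**Step 3: error against the true value t.** Substituting 0 gives −k·t/16, and substituting x gives +k·(x − t)/16. With k = 4 and x = 0.9:

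- t = 0.88: −4 × 0.88/16 = −0.22 against +4 × 0.02/16 = +0.005.
- t = 0.80: −4 × 0.80/16 = −0.20 against +4 × 0.10/16 = +0.025.

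The advantage of x depends on t, but it is large whenever t lies much closer to x than to 0.

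**Step 4: flags.** The SAP rule flags low whenever LLN > 0. What the record supports is this:

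| Recorded | Limits (assumed) | SAP flag | Certainly low? |
|---|---|---|---|
| `<0.2` | LLN 0 | none | no |
| `<0.2` | LLN 0.1 | low | no |
| `<0.2` | LLN 0.2 | low | yes |
| `≤1.005` | LLN 1.003 or 1.005 | low | no |
| `≤1.005` | LLN 1.010 | low | yes |

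The low flag is therefore unsupported when x > LLN > 0, and also when x = LLN for `≤x`. Otherwise it is right, or no flag arises.

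The high side has a smaller gap. A result `>x` with x equal to the upper limit of normal (ULN) is certainly high, but after substitution it sits exactly on the limit and is not flagged.

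**The case against.** The strongest reply is that the harm is hypothetical. Nothing in the documents shows that any INR, prothrombin time or partial thromboplastin time will be reported as `<x`. That stands, and it makes every figure above an illustration.

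Several stronger readings are tempting, and the documents do not support them:

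- **Urine specific gravity of 0 in the tables.** Appendix 2 does list "pH and specific gravity", but urinalysis is not summarized and listings show the recorded result. A 0 would serve only internally, to derive a flag. The SAP does not say which value is used for the changes shown in listings, so a listed change near −1 cannot be asserted.
- **All low flags are false.** Step 4 shows that many are correct. The recorded value and the clinical-significance assessment also appear in the listing.
- **Near-zero analytes are clearly distorted.** Suppose 8 of 16 subjects move from direct bilirubin `<0.1` to 0.1 mg/dL (assumed limit). The true mean rise lies between 0 and 8 × 0.1/16 = 0.05. The SAP rule shows 0.05 and substituting x shows 0. Neither is plainly better.
- **A warfarin safety signal is hidden.** The concern with warfarin is prolonged clotting, for which high-censored results already take x. The low-side rule matters for that signal only if a baseline is censored low.
- **The distortion exceeds any plausible real effect.** The documents give no effect size or SD for comparison.

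What the reply does not remove is the rule itself: it is explicit, unrestricted and uncorrected, and it gives an impossible value whenever it meets a coagulation result reported as `<x`.

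**Conclusion.** The point holds in a limited form. As written, SAP 8.6.2 would enter any low-censored coagulation result as an impossible 0, and would flag low some results that the record does not show to be low. Under the assumption of one `<0.9` among 16 INR values, the minimum becomes 0 rather than 0.9, the SD 0.250 rather than 0.025, and that subject's change −1.0 rather than −0.1. How often this would happen is unknown, because the reporting limits are not in the documents.

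A reader might infer that the rule threatens the trial's conclusions. It does not. Laboratory data are descriptive, SAP 8.6.6 plans no inferential safety analysis, and the pharmacokinetic analysis has its own rules for values below quantification (SAP 8.5.1.3 and 8.5.2). Severity: minor.

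**What to change.** Replace the substitution sentence in SAP 8.6.2 with:

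> For summary statistics, including change from baseline, values recorded as `<x`, `≤x`, `≥x` or `>x` will be set to x. Listing flags will be derived from the recorded inequality: low if `<x` with x ≤ LLN, or `≤x` with x < LLN; high if `>x` with x ≥ ULN, or `≥x` with x > ULN. The value used for change from baseline in the summaries will also be used for the changes shown in the listings.

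The boundary cases matter: a result `<x` with x equal to LLN is certainly low and must keep its flag, as it does under the present rule.

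The cost is a short SAP edit and a small programming change. The downside is an upward bias for near-zero analytes of at most x per censored value, and a real rise from below x up to x would show as no change.

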8.6.3. Vital Signs Parameters

All vital signs parameters, with changes from baseline, will be listed; any value outside the clinical reference range will be flagged, and whether the out of range value was deemed clinically significant or not clinically significant will be indicated.

The observed results and change from baseline for all vital signs results will be summarized descriptively by treatment and timepoint.

8.6.4. 12-lead Electrocardiogram Parameters

All 12-lead ECG parameters, with changes from baseline, will be listed; any value outside the clinical reference range will be flagged, and whether the out of range value was deemed clinically significant or not clinically significant will be indicated.

The observed results and change from baseline for all 12-lead ECG parameters will be summarized descriptively by treatment and time point. QTcF values that are > 450 msec and increase from baseline > 30 msec will be flagged in the data listing.

8.6.5. Other Assessments

Medical history and physical examination will be listed. Any physical examination abnormalities reported will also be flagged as clinically significant or not clinically significant as indicated.

All other safety and tolerability assessments not detailed in the above sections will be listed only.

8.6.6. Safety and Tolerability Statistical Methodology

No inferential statistical analyses are planned.

9. INTERIM ANALYSES

No interim analyses are planned.

10. SIGNIFICANT CHANGES FROM THE PROTOCOL-SPECIFIED ANALYSES

There were no significant changes from the protocol-specified analyses.

12. APPENDICES

Appendix 1: Document History

Status, Version	Date of Change	Summary/Reason for Changes
Final, Version 1.0	NA	NA; the first version.

NA = not applicable
